#### 7.8.2.1 Definitions related to adverse events

Pre-Treatment adverse event: Any AE with date and time of onset prior to the first injection of study medication. Pre-treatment AEs might also be termed Screening Period AEs.

Treatment emergent AE (TEAE): Any AE with date and time of onset after first injection of study medication. In case of (partially) missing date or time that could indicate a TEAE, it will be analysed as treatment emergent.

TEAEs during the treatment period: Any AE with date and time of onset after first injection of study medication and up to and including date of last injection of study medication + 28 days.

Adverse Drug Reactions (ADRs): Any AE that is possibly, probably or definitely related to study medication or the assessment of the relationship to study medication is missing as reported in the eCRF.

Adverse events related to study procedure: Any AE that was documented with causal relationship to a study procedure of "yes" in the eCRF.

Adverse events of special interest (AESI): Any AE that was documented as "AESI confirmed by Adjudication Committee" in the eCRF.

Local AE: Any AE that is documented with the category "Local (injection site) adverse event" in the eCRF.

Systemic AE: Any AE that is documented with the category "Systemic adverse event" in the eCRF.

Other AE: Any AE that is documented with the category "Other adverse event" in the eCRF, i.e. any adverse event that is neither local nor systemic.

AEs leading to premature discontinuation of treatment: Any AE for which action taken is documented as "Permanent discontinuation of the IMP" in the eCRF.

AEs leading to temporary discontinuation of treatment: Any AE for which action taken is documented as "Temporary discontinuation of the IMP" in the eCRF.

AEs leading to premature discontinuation of study: for which action taken is documented as "Withdrawal from the Study" in the eCRF.

Duration of adverse event (expressed in [days]) is calculated as follows:

- End date/time of AE onset date/time of AE
- In case of missing onset time or missing end time: end date of AE onset date of AE +
- In case of (partially) missing onset date or (partially) missing end date no calculation will be done

In case of ongoing end date/time (outcome = recovering, not recovered or unknown), date of study termination will be used as documented at the end of the study page or the early termination page of the eCRF.

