# 7.5 Prior and concomitant medications, procedures and non-drug medical interventions

All prescription and over the counter medications for relief of allergy symptoms taken over the last 2 years and those used for other conditions in the last 1 month before screening should be recorded in the eCRF. Details of any concomitant medication used during the clinical trial including all prescription and over the counter medications taken by the subject during the clinical trial until end of study (EoS) must be documented in the eCRF at each visit (scheduled or unscheduled).

All prior and concomitant medications documented in the eCRF will be coded using the World Health Organisation (WHO) Drug dictionary according to the version and the update strategy as defined in the coding guideline for this clinical trial.

All prior and concomitant procedures and non-drug medication interventions documented in the eCRF will be coded using the medical dictionary of regulatory activities (MedDRA) according to the version and update strategy as defined in the coding guideline for this clinical trial.

Prior medications are defined as medications that started prior to first injection of investigational drug/placebo. In case the start date is missing or incomplete with the possibility that the medication was taken prior first injection of investigational drug/placebo, it will be assumed that at least one dose was taken prior to the first injection of investigational drug/placebo and thus the entry will be considered as prior medication.

Concomitant medications are defined as any medication with at least one dose taken at or after the first injection of investigational drug/placebo, i.e., for all end dates larger or equal to first documented injection of investigational drug/placebo. In case the end date is missing or incomplete with the possibility that the medication was taken after the first injection of investigational drug/placebo, it will be assumed that at least one dose was taken after the first injection of investigational drug/placebo and thus the entry will be considered as concomitant medication.

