#### 7.8.2 Adverse events

All Adverse events during the course of the study will be coded using the medical dictionary of regulatory activities (MedDRA) current at the start of the study and summarised by treatment group. AEs will be summarised by treatment, primary system organ class (SOC), preferred term (PT), relationship assessment and severity.

All solicited AEs identified via separate phone calls for the US will also be entered in the general AE section of the eCRF. Therefore, no separate analysis will be conducted.

The SOCs as well as the PTs within each summary table will be sorted by frequency in the total column in decreasing order.

AEs will be reported separately as pre-treatment or screening period AEs (any AE occurring prior to the first injection of study medication) and treatment emergent AEs (any AEs after first injection of study medication).

In general, all adverse events will be listed by treatment group, subject number, and period. For AE onset and end dates, the study day relative to the first injection will be listed.

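### An adverse event timed exactly at the first injection is neither pre-treatment nor treatment-emergent, so the TEAE-labelled tables would not reconcile with the other AE outputs

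*SAP*

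**What the plan says.** SAP 7.8.2 (Adverse events) divides events into two reporting classes at the first injection: "any AE occurring prior to the first injection of study medication) and treatment emergent AEs (any AEs after first injection of study medication".

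SAP 7.8.2.1 repeats the split using date and time:

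- Pre-treatment AE: "Any AE with date and time of onset prior to the first injection of study medication".
- TEAE: "Any AE with date and time of onset after first injection of study medication. In case of (partially) missing date or time". The second sentence is the only default rule: "In case of (partially) missing date or time that could indicate a TEAE, it will be analysed as treatment emergent".
- Treatment-period TEAE: "Any AE with date and time of onset after first injection of study medication and up to and including date of last injection", extended by 28 days. The lower limit is again exclusive, while the upper limit is expressly inclusive.

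The ADR definition in the same section depends on the relationship assessment (related, or assessment missing) and sets no condition on onset time.

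For a different kind of data, SAP 7.5 includes the boundary. Concomitant medication is "any medication with at least one dose taken at or after the first injection of investigational drug/placebo".

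**The concern.** The two AE classes are meant to cover all events, but as worded they leave out one point: an onset recorded at the time of the first injection. Where times are kept to the minute, a reaction noticed as the injection is given could be entered with the injection time. The default rule does not help, because nothing is missing. The result is perverse, since the better-documented event loses its TEAE status and the same event with a blank time keeps it.

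The frequency and severity of AEs and the frequency of AESIs are stated safety endpoints. At stake is whether the tables that report them are complete at this boundary and agree with each other. Two programmers could also code the boundary differently, and the SAP gives no basis for choosing between them.

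**Working it through.** The plan states no figure on this point and no arithmetic applies. The check is a partition of onset time t against first-injection time t0, followed by tracing the unassigned case through the planned outputs.

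**Step 1: classification under SAP 7.8.2 and 7.8.2.1**

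| Recorded onset | Class under the text |
|---|---|
| t < t0 | Pre-treatment |
| t > t0 | TEAE |
| t missing or partial, possibly after t0 | TEAE (default rule) |
| t = t0, fully recorded | None |

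**Step 2: where the unassigned event appears, taking table labels as written**

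It is absent from:

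- in the SAP section on summary tables for AEs (also numbered 7.8.2): TEAEs, treatment-emergent SAEs, treatment-emergent AESIs, TEAEs leading to discontinuation of treatment or study, and the severity and relationship display for all TEAEs;
- in SAP 7.8.2.2: the local, systemic and other TEAE rows.

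It is present in:

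- the ADR, serious ADR and ADR-discontinuation tables, if related or if the relationship is missing;
- the local, systemic and other AE tables, and the severity and relationship display for all SAEs;
- the SAP 7.8.2.2 rows for any AE, severe AE, AESI, serious or non-serious AE, and AEs leading to discontinuation, wherever the event qualifies;
- the listings.

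**Step 3: consequences for reconciliation**

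- A related serious event tied at t0 counts as a serious ADR but not as a treatment-emergent SAE.
- A local event tied at t0 counts in the local AE table but not in the overview row for local TEAEs.
- A confirmed AESI tied at t0 counts in the overview AESI row but not in the treatment-emergent AESI table.

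**Step 4: reach**

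The Protocol (Overall Design) plans six injections. Only the first sets t0. An onset at the time of any of injections 2 to 6 already satisfies t > t0 and is a TEAE. The gap is therefore limited to fully timed ties at one injection of six.

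**Step 5: effect of the fix**

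If TEAE means t ≥ t0 and pre-treatment means t < t0, every fully recorded onset falls into exactly one class and the mismatches in step 3 disappear.

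**The case against.** The strongest reply is that the intent is clear. SAP 7.8.2 offers two classes and no third, a reaction caused by an injection must follow it, so a recorded tie reflects rounding to the minute, and the default rule resolves uncertain timing towards TEAE. A sensible programmer might code the boundary as inclusive. This is fair as a reading of intent, but the text does not say it, and the default rule is confined to incomplete dates or times.

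It can also be said that a timing convention may exist in documents not seen here. The protocol supplied is abbreviated: SAP 7.7.1.1 cites a protocol section 9.3.5.1 that it does not contain. That possibility stands. The SAP definitions would still be better complete in themselves.

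The contrast with SAP 7.5 should not be pressed. That rule works on end dates, concerns medication, and allows prior and concomitant use to overlap. It shows that the SAP states an inclusive boundary where it wants one. It does not contradict the AE rule.

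A reader might go further and infer that immediate reactions in general vanish from the safety report, that more are lost in the active arm, and that the product therefore looks better tolerated than it is. The documents do not support this. Reactions at injections 2 to 6 are unaffected, the retained outputs in step 2 still show the event, and nothing in the documents says how often onset is entered as the injection time or how that differs by arm. Any count of affected subjects would rest wholly on an assumed rate. It would also overstate the loss in subject-level tables, because a subject with the same preferred term after a later injection is still counted.

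**Conclusion.** The gap is real on the wording and narrow in reach. A fully timed onset equal to the first-injection time has no class. Applied literally, the rule removes it from the treatment-emergent outputs alone, so that these fail to reconcile with the ADR, AE and SAE outputs that keep it. The number of such events, and whether they favour either arm, cannot be derived from the documents; it may be zero. The conclusion assumes that the definitions are applied as written, that the table labels mean what they say, and that no timing convention elsewhere settles ties. This is a drafting correction to a stated rule, worth making because it is so cheap. It is not evidence of biased safety reporting.

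**What to change.** In SAP 7.8.2 and 7.8.2.1, define TEAE as onset at or after the date and time of the first injection, and make the same change to the lower limit of TEAEs during the treatment period. Leave pre-treatment as strictly before the first injection. The default rule for incomplete timing can stay as it is.

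The cost is a few words in the SAP and one comparison operator in the program, with no effect on trial conduct. The downside is that TEAE counts may rise slightly, including by an event that began by coincidence at the injection time. The change should be made before unblinding, so that results cannot influence the choice.

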**Period 4** (Telephone safety follow-up): This consists of safety telephone calls at approximately 12 weeks and 24 weeks after the last injection to ascertain occurrence of any AEs.

**Target population:** Adult (18 to 65 years inclusive) subjects with seasonal allergic rhinitis and/or rhinoconjunctivitis due to grass pollen exposure (with or without allergic asthma that is well controlled).

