## 7.8.2 Summary tables for analysis of adverse events

The number and percentage of subjects with

- TEAEs
- ADRs
- treatment emergent serious adverse events (SAEs)
- serious ADRs
- treatment emergent adverse events of special interest (AESIs)
- TEAEs leading to premature discontinuation of treatment
- ADRs leading to premature discontinuation of treatment
- TEAEs leading to temporary discontinuation of treatment
- ADRs leading to temporary discontinuation of treatment
- TEAEs leading to premature discontinuation of study

- ADRs leading to premature discontinuation of study
- local AEs
- systemic AEs
- other AEs, not classified as local or systemic AEs

will be summarised by treatment group, MedDRA SOC and PT.

For the analysis of the severity and the relationship of AEs, the worst severity and the strongest relationship per subject and type of AE will be used. The number and percentage of subjects with at least one AE by MedDRA SOC, PT and severity/relationship will be displayed only for

- all TEAEs
- all ADRs

all serious adverse events (SAEs).

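### The TEAE definition rests on onset alone, so an AE that starts in screening and worsens or becomes serious after an injection is left out of the TEAE-restricted tables

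*SAP*

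**What the plan says.** SAP 7.8.2.1 sorts adverse events by their onset relative to the first injection.

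- Pre-treatment AE: "Any AE with date and time of onset prior to the first injection of study medication".
- TEAE, with its one extension, which concerns incomplete dates: "Any AE with date and time of onset after first injection of study medication. In case of (partially) missing date or time that could indicate" emergence, the event is counted as a TEAE.
- The narrower class of TEAEs during the treatment period also goes by onset, with the window running "up to and including date of last injection of study medication + 28 days".

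The introductory text of SAP 7.8.2 (Adverse events) makes the same split. Its pre-treatment class is "any AE occurring prior to the first injection of study medication". Its treatment-emergent class is worded more loosely, as AEs after the first injection.

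The ADR definition in 7.8.2.1 has no onset condition. It depends only on the relationship being possible, probable, definite or missing.

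The Protocol's Schedule of activities has AEs collected from Visit 1, while the first injection is at Visit 2.

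**The concern.** AEs can start in the interval between Visit 1 and the first injection, and some will still be present at Visit 2. If such an event becomes more severe or serious after an injection, or leads to discontinuation, the change happens under treatment. The definition looks only at when the event began, so the event stays in the pre-treatment class. No section of the supplied documents counts worsening as treatment-emergent or says that it is entered as a new AE.

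Frequency and severity of AEs, AEs leading to premature discontinuation, and AESIs are stated safety endpoints (Protocol, Objectives and Endpoints; SAP Table 1). The treatment-emergent tables are the natural place to read these by arm. Under the rule as written they undercount post-injection aggravation, and they need not agree with other tables in the same report.

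**Working it through.** The documents give no figure that depends on this rule, so there is nothing to reproduce. The check is to apply the 7.8.2.1 definitions to test cases and follow each through the tables listed in SAP 7.8.2 (Summary tables for analysis of adverse events) and 7.8.2.2 (Overview summary tables).

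| Case | Class under 7.8.2.1 | Tables that leave it out | Tables that can still show it |
|---|---|---|---|
| A. Complete onset date and time in screening; mild, then severe after an injection | Pre-treatment | TEAEs; TEAEs by severity | Overview rows for any AE and any severe AE; ADR tables if related or relationship missing |
| B. Complete onset in screening; becomes serious after an injection | Pre-treatment | TEAEs; treatment-emergent SAEs | All SAEs by severity and relationship; overview row for any serious AE; serious ADRs if related or relationship missing |
| C. Complete onset in screening; worsens after an injection, judged related, treatment permanently stopped | Pre-treatment | TEAEs; TEAEs leading to premature discontinuation of treatment | ADRs leading to premature discontinuation of treatment; the matching overview rows |
| D. Onset date or time missing or partial, possibly after the first injection | TEAE | None | All |

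An adjudicated AESI with screening onset follows the same path as B: it is outside the treatment-emergent AESI table but can be in the overview row for AESIs.

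Three things follow.

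1. With a complete onset before the first injection, no later course of the event brings it into a TEAE table. The rule that the worst severity per subject is used does not help, because in the TEAE severity table it works only among events already classed as TEAEs.
2. The tables stop nesting. Case C is an ADR leading to discontinuation that is not a TEAE leading to discontinuation. Case B is in the all-SAE table but not in the treatment-emergent SAE table.
3. The effect on the arm comparison is conditional. For a given TEAE row, let m_A and m_P be the proportions of subjects on PQ Grass and placebo whose only qualifying event is one left out by the rule. Then

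   tabulated risk difference = risk difference with worsening counted − (m_A − m_P).

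   If m_A = m_P, the risk difference is unchanged. If m_A > m_P, an excess on PQ Grass is understated by m_A − m_P. Neither quantity can be obtained from the documents.

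**The case against.** Several objections have force.

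- **The event stays in the report.** The ADR tables, the all-SAE table by severity and relationship, several overview rows and the listings are not worded as treatment-emergent. A reader might infer that the comparison of serious and discontinuation events misses the worsening altogether. The documents do not support that. One reservation is that section 7.8.2 also says pre-treatment AEs are reported separately, so the scope of the overview rows is not fully clear.
- **Pre-existing asthma is mostly not the issue.** The Protocol admits subjects "with or without allergic asthma that is well controlled", and it is tempting to argue that aggravated asthma would be hidden. But asthma and allergy present at screening are recorded as medical history or concurrent disease (SAP 7.4.1 and 7.4.3 to 7.4.5), not as screening AEs. If such a condition worsens after an injection and is reported as an AE, there is no earlier AE record, its onset as an AE is after the injection, and it is a TEAE. The gap is confined to AEs that newly arise between Visit 1 and the first injection.
- **A recording rule may exist elsewhere.** The supplied protocol is a synopsis, and the SAP cites a protocol section that is not in it. If the fuller protocol or the eCRF instructions require a new AE record on worsening, the gap closes. Nothing supplied shows this, and the fix allows for it.
- **Rare-event effects.** A reader might infer that one or two missed events would distort counts of rare serious events. The documents give no rate of ongoing screening AEs, of worsening, or of serious events among those that worsen, so no percentage can be defended.

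These objections limit the consequence. They do not change the classification, which follows directly from 7.8.2.1.

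**Conclusion.** The point stands in limited form. This is a stated rule that misclassifies a definable kind of event, rather than a detail left unsaid. The TEAE-restricted tables would leave out post-injection aggravation of AEs that began in screening, and would disagree with the ADR and all-SAE tables.

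The number of subjects cannot be derived and is probably small, since an event must arise in screening, persist to the first injection and then worsen. Bias toward no difference in the TEAE comparison should not be asserted outright: it requires that such worsening be more frequent on PQ Grass than on placebo.

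The conclusion assumes that no recording rule outside the supplied documents turns a worsening into a new AE. The correction is cheap and worth making before unblinding.

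**What to change.** In SAP 7.8.2.1, do one of the following:

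- define a TEAE as any AE with onset at or after the first injection, or with earlier onset and an increase in severity or a change to serious at or after the first injection, and use the post-injection severity for such events in the severity table; or
- state that such worsening is entered as a new AE record with its own onset date and time, citing the recording rule if one already exists.

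Apply the choice to every treatment-emergent table (SAEs, AESIs, discontinuations, severity) and bring the wording of section 7.8.2 into line. Say also how the tables treat a screening-onset AE that leads to discontinuation after an injection without a recorded change in severity or seriousness, because the first option alone would leave it as pre-treatment. Wording it as at or after the first injection also places an AE timed exactly at the injection, which the present before/after wording assigns to neither class.

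The text change is a sentence or two. The real cost lies in the data: changes in severity or seriousness of AEs ongoing at Visit 2 must be dated or re-entered, and the documents do not show whether those dates are collected. TEAE counts may rise slightly.

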#### **Overall Design (Brief Summary):**

This is a multi-centre, randomised, parallel group, double-blind, placebo-controlled clinical trial to confirm the efficacy and safety of the optimal effective dose of PQ Grass (27600 SU). The trial will have an adaptive group sequential design with one planned interim analysis.

Subjects will be assigned in a ratio of 1:1 (PQ Grass:Placebo) with treatment course to be completed prior to the onset of the grass pollen season (GPS):

- **PQ Grass:** 6 injections of PQ Grass (900, 2700, 6000, 6000, 6000, 6000 SU sequentially) *or*
- **Placebo:** 6 injections of placebo

The study includes 4 periods, encompassing 11 visits to the study site and at least 2 follow-up telephone calls. Subjects will be provided with enough relief medication to cover them through this period by the study site.

**Period 1** (Screening [Visit  $1 \pm \text{Visit 1a}$ ]): This includes the screening visit at which subjects' eligibility for the clinical trial will be assessed.

**Period 2** (Randomisation and treatment [Visit 2 to Visit 7]): At Visit 2, subjects will be randomly allocated in a randomisation ratio of 1:1 to the active treatment (PQ Grass) or the placebo treatment group and will receive the first injection.

After Randomization at Visit 2, subjects will thereafter return to the study site at subsequent visits during the treatment period (Visit 3 to Visit 7) to receive the remaining injections. The average duration of the treatment period will be approximately 16 weeks.

Treatment with either 6 injections of active treatment (900, 2700, 6000, 6000, 6000 and 6000 SU sequentially) to achieve a cumulative nominal dose of 27600 SU, or 6 injections of placebo will be administered prior to the onset of the GPS.

**Period 3** During the GPS, subjects will record their allergic rhinitis/rhinoconjunctivitis symptoms and use of relief medications in an electronic diary (eDiary). The symptom and medication scores during the peak GPS and the entire (or truncated) GPS calculated according to the European Academy of Allergy and Clinical Immunology (EAACI) recommendations for the CSMS (primary endpoint) will be compared between the active and placebo treatment groups. The following 4 visits will be performed:

- Visit 8 (pre-GPS)
- Visit 9 ( $\approx$  onset of GPS)
- Visit 10 (during GPS)
- Visit 11 ( $\approx$  end of GPS)

Protocol: PQGrass306

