## 7.8.2.2 Overview summary tables for adverse events

An overview summary of the following AE types will be provided, presenting number and percentage of subjects experiencing at least one AE of the respective AE type in each treatment group as well as the corresponding number of events.

- Any AE
- Any ADR
- Any severe AE
- Any severe ADR
- Any AE of special interest
- Any serious AE
- Any serious ADR
- Any non-serious AE
- Any AE leading to premature discontinuation from treatment
- Any AE leading to temporary discontinuation from treatment
- Any ADR leading to premature discontinuation from treatment
- Any ADR leading to temporary discontinuation from treatment
- Any AE leading to premature discontinuation of study
- Any ADR leading to premature discontinuation of study
- Any local TEAE
- Any systemic TEAE
- Any other TEAE, not classified as local or systemic AE

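### The SAP defines treatment-period adverse events but no table uses them, so six AE table types and the TEAE severity tables mix the injection phase with about 20 later weeks and dilute its between-arm contrast

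*SAP*

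**What the plan says.** SAP 7.8.2.1 gives two definitions. A TEAE is "Any AE with date and time of onset after first injection of study medication", with no upper limit. A treatment-period TEAE has onset "after first injection of study medication and up to and including date of last injection of study medication + 28 days". The second term does not appear again.

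In the text of SAP 7.8.2, "AEs will be reported separately as pre-treatment or screening period AEs" and as treatment-emergent AEs, with no further split by time. The section on summary tables lists 14 AE types that "will be summarised by treatment group, MedDRA SOC and PT". It adds severity and relationship tables for TEAEs, adverse drug reactions (ADRs) and serious AEs, taking each subject's worst severity per type of AE. SAP 7.8.2.2 opens with "An overview summary of the following AE types will be provided" and lists 17 rows. No entry in either list is limited to the treatment period. Trial period appears only in the listings (SAP 7.1.2 and 7.8.2).

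The protocol's Overall Design places all injections before the start of the pollen season. Period 4 then provides "safety telephone calls at approximately 12 weeks and 24 weeks after the last injection", and the Schedule of activities shows AE collection at every visit and at both calls.

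**The concern.** The safety objective covers the frequency and severity of AEs and their relationship to treatment. Reactions to the injections would be expected mainly while injections are being given. Subjects are then observed through a pollen season and further follow-up without dosing. A subject with any event in either phase counts once in the pooled row, so background events in the later phase raise both arms' percentages and shrink the visible contrast from the injection phase. Severity is affected in the same way: a severe event in the season replaces a mild injection-phase event of the same type in that subject.

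The SAP already has the definition that would separate the phases, but the tables as listed never use it. Nor is there another injection-phase view by onset: solicited US events are merged into the general AE section with no analysis of their own, and the listings give no between-arm frequency.

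**Working it through.** The documents give no AE rates, so there is no planned figure to reproduce. The check has three steps.

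**1. Which rows are exposed.** Of the 14 SOC/PT types:
- Eight are little affected: four on permanent or temporary discontinuation of study drug (these arise while injections are ongoing), one on local injection-site AEs, and three further ADR rows (all ADRs, serious ADRs, ADRs leading to study discontinuation).
- Six are exposed: all TEAEs, serious AEs, AEs of special interest, TEAEs leading to study discontinuation, systemic AEs and other AEs. The TEAE severity tables are exposed too.

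**2. How much of the TEAE window lies outside the treatment period.** Inputs: treatment duration T of approximately 16 weeks on average (Protocol, Overall Design) or 11 to 18 weeks (Protocol, Reference Therapy); treatment-period window to last injection + 28 days = T + 4 weeks; AE collection to T + 24 weeks.

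| T (weeks) | Treatment-period window | TEAE window | Share inside | Share after |
|---|---|---|---|---|
| 11 | 15 | 35 | 43% | 20/35 = 57% |
| 16 | 20 | 40 | 50% | 20/40 = 50% |
| 18 | 22 | 42 | 52% | 20/42 = 48% |

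**3. Effect on the contrast.** Let p be the proportion with an event in the treatment period and b the proportion with an event afterwards, with b equal in both arms and later events independent of treatment-period events. Then:

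- pooled proportion = 1 - (1 - p)(1 - b)
- pooled risk difference = (1 - b) × (p_active - p_placebo)

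Assume p = 10% active and 5% placebo, so the treatment-period risk ratio is 2.00 and the difference 5 points. At b = 20%, active is 1 - 0.90 × 0.80 = 28.0% and placebo is 1 - 0.95 × 0.80 = 24.0%. The ratio is 28.0/24.0 = 1.17 and the difference 0.80 × 5 = 4.0 points. Over a range of b:

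| b (assumed) | Active | Placebo | Difference (points) | Risk ratio | Nominal power |
|---|---|---|---|---|---|
| treatment period only | 10.0% | 5.0% | 5.0 | 2.00 | 0.61 |
| 2% | 11.8% | 6.9% | 4.9 | 1.71 | 0.51 |
| 5% | 14.5% | 9.75% | 4.75 | 1.49 | 0.40 |
| 10% | 19.0% | 14.5% | 4.5 | 1.31 | 0.29 |
| 20% | 28.0% | 24.0% | 4.0 | 1.17 | 0.19 |
| 40% | 46.0% | 43.0% | 3.0 | 1.07 | 0.11 |

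For 30% vs 20%, the ratio of 1.50 (power 0.78) falls to 1.40 (0.70) at b = 5% and 1.12 (0.29) at b = 40%. Power is for a two-sided 5% comparison with 277 per arm (555 randomised 1:1 in Year 1). It is only a yardstick for visibility, because the SAP plans summary statistics and no safety test.

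**The case against.** **The lists may not be a full inventory.** The SAP promises separate reporting of pre-treatment AEs and defines procedure-related AEs, yet neither has a row. The public SAP is abridged, and an unseen table shell could use the term. This stands as a caution. But both lists read as complete, and the written plan does not commit to the output.

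**Many rows are safe.** A reader might infer that every between-arm AE frequency is distorted. The documents do not support that, since eight of the 14 SOC/PT types are little affected. ADR and relationship tables also serve the stated endpoint directly, under double-blind assessment. They do rest on investigator judgement, however, so they do not replace a comparison by onset.

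**Dilution is not concealment.** With assumed rates of 50% vs 25% in the injection phase and 40% later in both arms, the pooled figures are 1 - 0.50 × 0.60 = 70% and 1 - 0.75 × 0.60 = 55%. A 15-point excess remains plain. This stands: the loss matters most where the later background is high relative to the injection-phase rate.

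**Reversal.** A reader might infer that PQ Grass, by reducing seasonal symptoms, could cancel or reverse an injection-phase excess. For example, 6% vs 3% followed by 8% vs 12% pools to 1 - 0.94 × 0.92 = 13.5% vs 1 - 0.97 × 0.88 = 14.6%. That needs seasonal symptoms to be recorded as AEs. The documents place them in the eDiary as efficacy data and do not say that they are also AEs, and the rates are invented. Reversal is not shown.

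**The split can be rebuilt.** Listings by period with study day lose no data. True, but a listing does not give the reader a between-arm summary.

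**Conclusion.** The point holds as a cheap improvement. It is certain from the text that the treatment-period definition appears in neither list of AE tables and that the TEAE definition has no end date. It follows that the exposed tables pool the injection phase with about 20 further weeks, roughly half of the TEAE window.

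The size of the dilution is not known. The factor (1 - b) on the risk difference rests on equal later incidence in both arms and on independence, and every rate used is an assumption. If the same subjects tend to report events in both phases, the relevant b is the later incidence among those with no injection-phase event. That is lower, and the dilution is less. For rare terms the loss is modest (risk ratio 1.71 at b = 2%); for broad rows such as all TEAEs it can be large. Under these assumptions the direction of effect does not change. Trial conduct and efficacy inference are unaffected.

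**What to change.** In SAP 7.8.2 (summary tables) and 7.8.2.2 (overview), add rows and SOC/PT tables restricted to the treatment period as already defined in 7.8.2.1, for all TEAEs, serious AEs, AEs of special interest, TEAEs leading to study discontinuation, systemic AEs and other AEs, with TEAE severity. Add matching tables for events with onset after that period; a subject with events in both counts once in each. Keep the pooled tables as planned. Report both windows and make neither the sole basis of the safety statement, because the 24-week follow-up exists to capture late events.

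The cost is SAP wording, an onset-date filter, a rerun of programmed tables, and more output to read. No new data are needed. One limit remains: the documents give no minimum gap between the last injection and season onset, so the 28 days may run into the early season. The split reduces the mixing but may not remove it.
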